**Notes for the Schedule of Assessments for Study Period 1 and Study Period 2:**

- After up to 2 months of Screening, the duration for an individual subject is expected to be 24 weeks in Study Period 1 and 28 weeks in Study Period 2. The maximum study duration in the open-label Study Period 3 may be approximately 7 years; however, subject participation will end if the drug becomes available or if there is no longer benefit from the study drug. For subjects not eligible to participate in Study Period 3, study duration will be up to 56 weeks (including the Follow-up Telephone Call).
- Study Period 1 starts at the Baseline Visit and continues to Week 25. Baseline assessments must be completed before the Week 1 assessments. Study Period 2 starts after the assessments at the Week 25 Visit and continues through the Week 53 Visit for subjects who are eligible and continue long-term treatment with IgPro20 in Study Period 3, or through the Week 56 Telephone Visit (EOP2) for subjects whose study participation ends with Study Period 2.
- For subjects who discontinue IMP early during participation in Study Period 1 or Study Period 2, all Week 53 assessments will be performed at the study visit where IMP treatment is discontinued instead of the assessments scheduled for that particular study visit.
- Confirmation per Treating and Evaluating Physicians that no clinically relevant improvement has occurred since Screening and that the subject is still eligible for the study.
- This study assessment will not be performed at any study visit after discontinuation of IMP treatment.
- Additional IMP will be assigned at UNS Visit if the subject's weight has increased (> 2 kg), which will require a dose volume increase (see [Appendix 15](#)).
- Only if subject is eligible for continuation of treatment in Study Period 3.
- Vital sign assessments include supine systolic and diastolic blood pressure, pulse rate, respiratory rate, and body temperature.
- Safety assessments: Monitoring for corticosteroid treatment, monitoring for TEEs (including Wells' Criteria score for DVT and/or Wells' Criteria score for PE), monitoring for hemolysis at Week 2 and Week 5 only.
- Urine hCG pregnancy test is to be completed for all premenopausal females capable of becoming pregnant. This includes women on oral, injectable, or mechanical contraception and women whose partners have been vasectomized or have received or are utilizing mechanical contraceptive devices.
- Additional laboratory collection for Week 37 is located in [Schedule of Assessments for Rich Pharmacokinetic Sampling](#).
- Optional DNA blood samples for exploratory biomarkers.
- Hematology: hemoglobin, hematocrit, platelets, erythrocytes, leukocytes with differential counts (neutrophils, basophils, eosinophils, lymphocytes, monocytes).
- Muscle enzymes: CK, LDH, AST, ALT, aldolase.

- O. Hemolysis: DAT, total bilirubin, direct bilirubin, indirect bilirubin, haptoglobin, reticulocytes, and peripheral blood smear to check for spherocytosis. Peripheral blood smear will be performed at Week 2 and Week 5 only.
- P. Other biochemistry: sodium, potassium, chloride, bicarbonate, BUN, glucose, GGT, alkaline phosphatase, creatinine.
- Q. Coagulation: D-dimer complex.
- R. MSA and MAA: anti-Jo-1, anti-PL-7, anti-PL-12, anti-EJ, anti-OJ, anti-SRP, anti-Mi-2, anti-p155/140, anti-TIF-1 $\gamma$ , anti-MDA5, anti-NXP-2, anti-PM/Scl, anti-Ro-SSA, anti-Ku, anti-U1 RNP, anti-U3 RNP, anti-HMGCR, anti-SAE-1Ab.
- S. Retention samples at Baseline and Week 53/end of study participation. A virology retention sample should be obtained for all subjects who discontinue at any time during the study.
- T. IMP SC infusions at Week 1 and Week 2 are to be administered only after the visit-specific assessments (except SC infusion diary review) are completed.
- U. Training and supervised IMP SC infusions at the site on Week 1 and Week 2. If additional infusion training at the site is requested by the subject for Week 3 and/or Week 4, no other UNS Visit assessments are required to be performed. Week 3 and Week 4 additional infusion training will be documented in the eCRF. After training is completed, IMP will not be administered during subsequent study visits. For the remainder of their participation in the study, subjects will self-administer IMP at home.
- V. Physiotherapy regimen may be modified starting at Week 17 if clinically relevant improvement is achieved.
- W. Only if subject discontinues IMP treatment before Week 25.
- X. IMP will only be administered at the site for unscheduled visits which occur at Week 3 or Week 4.
- Y. See [Section 5.3.1](#) for DOW criteria and corticosteroid rescue details (Week 9 to Week 25). DOW assessment at UNS Visit only if before Week 25.
- Z.  $\geq 2$  cm improvement from Baseline on 10-cm Physician Global Disease Activity VAS.
- AA. Six individual CSMs will be assessed during the study for TIS calculation: (1) Physician Global Disease Activity, (2) Patient Global Activity Assessment, (3) Manual Muscle Testing of 8 muscle groups (MMT-8), (4) HAQ, (5) Muscle Enzyme, and (6) Extramuscular Global Assessment.
- BB. TSQM-9 is not performed at Baseline.
- CC. The Week 56 Safety Follow-up Telephone Call will not be performed for subjects who discontinue IMP treatment before Week 53 but remain in the study for at least 1 subsequent study visit 4 weeks after IMP discontinuation or subjects who are eligible to continue treatment in Study Period 3.

**Table 3** Schedule of Assessments for Open-label Study Period 3

	Subsequent Years (4-week cycles)					
	Study Week	Every 4 weeks	Every 24 weeks	End of Year	UNS	EOP3
Time Window	±7d	±7d	±7d	NA	±7d	
Assessments						
Urine hCG pregnancy test B		X	X	X	X	
Physical examination			X			X
Vital signs C		X	X	X	X	
Body weight	X	X	X	X	X	
Virology retention sample						X
Hematology and biochemistry D, E			X	X	X	
Efficacy assessments (4 individual CSMs) F		X	X	X	X	
CDASI		X	X	X	X	
EQ-5D-5L		X	X	X	X	
IMP assignment G	X	X	X H			
IMP SC weekly infusions	X	X	X H			
Subject SC Infusion Diary Review	X	X	X	X	X	
AEs	◀				▶	
Concomitant therapies	◀				▶	

AE = adverse event; BUN = blood urea nitrogen; CDASI = Cutaneous Dermatomyositis Disease Area and Severity Index; CSM = core set measure; d = day

EQ-5D-5L = EuroQoL 5-Dimension Questionnaire; EOP3 = End of Study Period 3; GGT = gamma-glutamyl transferase; HAQ = Health Assessment Questionnaire; hCG = human chorionic gonadotropin; IMP = investigational medicinal product; M = month; MMT-8 = Manual Muscle Testing of 8 muscle groups; NA = not applicable; SC = subcutaneous; UNS = unscheduled visit; W = week.

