Key Secondary Endpoints	Key secondary endpoints of the study are: 

• TIS at Week 25

• Change from Baseline in Manual Muscle Testing (MMT-8) at Week 25

• Change from Baseline in Cutaneous Dermatomyositis Disease Area and Severity Index (CDASI) total activity score at Week 25

• Reduction of oral corticosteroid dose at Week 25

Secondary Endpoints	Additional secondary endpoints of the study are: 

• TIS from Week 5 to Week 53

• Individual core set measures (CSMs; except muscle enzyme), and CDASI from Baseline to Week 53

○ Physician Global VAS

○ Patient Global VAS

○ MMT-8

○ Health Assessment Questionnaire - Disability Index (HAQ-DI)

○ Extramuscular Global Assessment

• Definition of Worsening from Baseline to Week 53

• Reduction of oral concomitant corticosteroid dose from Baseline to Week 53

• Use of rescue corticosteroid treatment from Baseline to Week 25

• Mobility, Self-care, and Usual Activities domains of EuroQoL 5-Dimension Questionnaire (EQ-5D-5L) from Baseline to Week 53

• Treatment-emergent adverse events (TEAEs)

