Waist circumference	X								X								X			
IMP assignment E,F	X		X	X	X	X	X	X	X	X	X	X	X	X	X	X G	X H			
Vital signs H	X		X	X	X	X	X	X	X	X	X	X	X	X	X	X	X			
Safety assessments I	X		X	X	X	X	X	X	X	X	X	X	X	X	X	X	X			
Laboratory collections:																				
Urine hCG pregnancy test J	X			X	X	X	X	X	X	X	X	X	X	X	X	X	X			
Serum exploratory biomarkers E,K	X			X	X		X	X	X			X				X	X			
DNA exploratory biomarkers L	X																			
RNA exploratory biomarkers E	X			X					X								X			
Hematology M	X		X	X	X		X		X		X			X		X	X			
HbA1c	X								X								X			
Muscle enzymes N	X			X	X	X	X	X	X	X	X	X	X	X	X	X	X			
Additional labs for hemolysis criteria O	X		X	X																
Other biochemistry P	X				X		X		X		X			X		X	X			

Study Year	Year 1 A																	UNS	
Study Period	Study Period 1 B										Study Period 2 B								
Study Week	Base -line	W1	W2 ±3d	W5 ±3d	W9 ±3d	W13 ±3d	W17 ±3d	W21 ±3d	W25 EOP1 ±3d	W29 ±3d	W33 ±3d	W37 ±3d	W41 ±3d	W45 ±3d	W49 ±3d	W53 C ±3d	W56 EOP2 ±3d		
Assessments																			
Coagulation Q	X		X	X	X	X	X	X	X	X	X	X	X	X	X	X		X	
Serum IgG levels E	X		X	X	X		X	X	X			X			X	X		X	
Rich PK sampling E												X K							
ANA, MSA, and MAA E,R									X							X			
Virology retention sample E,S	X															X			
IMP SC infusion E,T,U		X	X	X-----X													X G	X X	
Subject SC Infusion Diary review E		X	X	X	X	X	X	X	X	X	X	X	X	X	X	X		X	
AEs	X																X	X	
Concomitant therapies		X															X	X	
Change to physiotherapy V	X		X	X	X	X	X	X	X	X	X	X	X	X	X	X		X	
DOW Y			X	X	X	X	X	X	X							X		X	
Assess for clinically relevant improvement Z	X						X	X	X	X	X	X	X	X	X			X	
Individual CSMs AA	X		X	X	X	X	X	X	X	X	X	X	X	X	X	X		X	
CDASI	X		X	X	X	X	X	X	X	X	X	X	X	X	X	X		X	
5-D Itch Score	X			X		X			X		X		X				X		
Timed Up and Go	X			X		X			X		X		X				X		
EQ-5D-5L, WPAI-GH, and TSQM-9 E,BB	X					X			X		X		X			X			
Review eligibility for open-label Study Period 3																X			

Study Year	Year 1 A																UNS
Study Period	Study Period 1 B										Study Period 2 B						UNS

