3	Use of rescue corticosteroid treatment from Baseline to Week 25	
 
Percentage of subjects receiving rescue corticosteroid treatment by treatment sequence and visit
 
Percentage of subjects whose rescue corticosteroid treatment is tapered by treatment sequence and visit
 
Time to first administration of rescue corticosteroid treatment
 

1, 3	Mobility, Self-care, and Usual Activities domains of EuroQoL 5-Dimension	
 
Number and percentage of subjects having at least 1 level, 2 levels, and <math>> 2</math> levels of improvement from Baseline by treatment sequence at Week 13 and Week 25
 

Secondary Objectives	Endpoints	Summary Measures
	Questionnaire (EQ-5D-5L) to Week 53	
 
Number and percentage of subjects having no reduction in levels, at least 1 level, 2 levels, and > 2 levels of improvement from Week 25 by treatment sequence at Week 41 and Week 53
 

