## 4.3 Discontinuation of IMP and Subject Study Withdrawal

### 4.3.1 Discontinuation of IMP

If any of the following apply, the subject must discontinue IMP:

- Subject wishes to discontinue IMP
- Subject withdraws consent for study participation
- Investigator advises that the subject's safety or well-being could be compromised by further treatment
- Subject or caregiver is not able to administer the SC infusions at home by Week 4
- Subject has confirmed diagnosis of DVT or PE
- Subject has Grade 3 hemolysis (see [Section 8.1.2.3](#))
- Subject becomes pregnant
- Relevant treatment noncompliance

During participation in Study Period 3, if the investigator determines that the subject is no longer benefiting from IgPro20 and/or is showing signs of clinical deterioration in DM status, the subject must be discontinued from the study.

The investigator should record in the electronic case report form (eCRF) and in the subject's medical records the reason and date of IMP discontinuation.

Subjects who discontinue IMP will be encouraged to remain in the study until Week 25 if discontinuation occurs during Study Period 1, or until Week 53 if discontinuation occurs during Study Period 2, in order to collect study assessments. The Safety Follow-up Telephone Call will not be performed for subjects who discontinue IMP treatment but remain in the study for at least 1 subsequent study visit 4 weeks after IMP discontinuation. See [Schedule of Assessments](#) for details on assessments no longer collected after IMP discontinuation if the subject remains in the study, and Section 4.3.2 for details on handling subject withdrawal from study.

Subjects who discontinue IMP during Study Period 3 will be withdrawn from the study. Withdrawal from IMP Study Period 1 or Study Period 2 renders a subject ineligible for participation in Study Period 3 of this study.

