## 10.5 Analysis of Secondary Efficacy Endpoint

All secondary efficacy analyses will be performed for the following periods and analysis sets:

- Week 1-25 by treatment sequence (mITT)
- Week 25-53 by treatment sequence (mITT-Ex)

Raw data and changes from the reference visit will be summarized at all visits as appropriate (Table 11). Comparison between treatment sequences will be performed using statistical models as described below. No imputation is planned for missing data in secondary endpoints. P-values from the statistical models are descriptive.

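### EQ-5D-5L collection ends when IMP is stopped, so the observed Week 13 and Week 25 improvement data describe essentially only subjects still on treatment, and the denominator is not stated

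*Protocol*

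**What the plan says.** The Protocol Synopsis lists as a secondary endpoint "Mobility, Self-care, and Usual Activities domains of EuroQoL 5-Dimension Questionnaire (EQ-5D-5L) from Baseline to Week 53". Protocol 2.2.3 summarises it in Study Period 1 as the number and percentage of subjects with given "levels of improvement from Baseline by treatment sequence at Week 13 and Week 25".

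In Protocol Table 2 the row is labelled "EQ-5D-5L, WPAI-GH, and TSQM-9 E,BB". Note E reads "This study assessment will not be performed at any study visit after discontinuation of IMP treatment". Note BB only says that TSQM-9 is not done at Baseline. The row "Individual CSMs AA" has no note E, and neither do the rows for CDASI, 5-D Itch and Timed Up and Go.

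Protocol 4.3.1 states: "Subjects who discontinue IMP will be encouraged to remain in the study until Week 25 if discontinuation occurs during Study Period 1". The stated purpose is to collect study assessments, and the section refers to the Schedule for those that stop. Protocol 8.5.6 says the same, and adds that the Week 53 set is done at the visit where IMP is stopped. That set includes the EQ-5D-5L (Protocol 8.5.4.7).

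SAP 7.2 assigns this stopping-visit set to EOT P1 when the stop falls in Study Period 1. SAP 10.5 analyses Weeks 1 to 25 on the mITT and says: "No imputation is planned for missing data in secondary endpoints". It compares the EQ-5D-5L domains with frequency counts and a Kolmogorov-Smirnov test. SAP 8.2.3 and Table 8 footnote a admit efficacy assessments only up to 7 days after IMP is stopped, and only if no rescue was given first.

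**The concern.** Stopping collection makes sense for TSQM-9, which asks about satisfaction with the medication being taken. The EQ-5D-5L asks about health on the day and has no such dependence on treatment. It seems to share the restriction because it shares a row. Exploratory outcomes, including the patient-reported itch score, stay scheduled after IMP is stopped, while a secondary efficacy endpoint does not.

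The result is selection on an event after randomization. If the two arms stop IMP at different rates or for different reasons, the subjects compared at Week 25 are no longer the groups that were randomized. The primary estimand deals with this event explicitly: a stop unrelated to the Ukraine war is a treatment failure (SAP 10.1). For the EQ-5D-5L no strategy is stated, and neither is the denominator of its percentages. A reader of the report could not tell which question the Week 25 figures answer.

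**Working it through.** **1. Which assessments continue after IMP is stopped (Protocol Table 2).**

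| Assessment | Endpoint status | Note E |
|---|---|---|
| Core set measures, including the self-reported HAQ | basis of the primary; five are also secondary | no |
| CDASI | key secondary | no |
| 5-D Itch, Timed Up and Go | exploratory | no |
| EQ-5D-5L: Mobility, Self-care, Usual Activities | secondary | yes (shared row) |
| TSQM-9, WPAI-GH | exploratory | yes (shared row) |

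Note E is the fifth in the list under Table 2. The third and fourth match C on the Week 53 column and D on the eligibility row, so the lettering is consistent.

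**2. Where a Study Period 1 stopper's EQ-5D-5L goes.** The one value at the stopping visit goes to EOT P1. Later visits have none, under note E. No imputation fills the gap. SAP 10.5 adds a last-individual-visit time point for continuous variables, but these domains are analysed as cumulative distributions. The Week 13 and Week 25 data therefore come essentially only from subjects on IMP. Rescued subjects who stay on IMP are still measured.

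**3. Illustration of size.** The documents give no figure for this endpoint. Their sizing figure, power of 0.905 at 126 subjects in SAP Table 14, reproduces as 0.904 by exact enumeration but has no bearing here. Only the 63 subjects per arm are taken from it. All other rates below are assumptions.

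- Improvement at Week 25 among those on IMP: pA = 40%, pB = 25%, an observed difference of 15.0 points.
- Proportion stopping IMP: dA on IgPro20, dB on placebo, from 5% to 20%.
- Improvement among stoppers: q, from 0 to 20%.

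All-subject difference = [(1 − dA)·pA + dA·q] − [(1 − dB)·pB + dB·q]

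| dA / dB | No Week 25 value, of 63 per arm | q = 0 | q = 10% | q = 20% |
|---|---|---|---|---|
| 5% / 5% | 3.2 / 3.2 | 14.3 | 14.3 | 14.3 |
| 10% / 10% | 6.3 / 6.3 | 13.5 | 13.5 | 13.5 |
| 20% / 20% | 12.6 / 12.6 | 12.0 | 12.0 | 12.0 |
| 20% / 10% | 12.6 / 6.3 | 9.5 | 10.5 | 11.5 |
| 10% / 20% | 6.3 / 12.6 | 16.0 | 15.0 | 14.0 |

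Example, 20% / 10% with q = 0: 0.80 × 0.40 − 0.90 × 0.25 = 0.320 − 0.225 = 0.095.

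**4. The denominator.** The q = 0 column is also what would be reported if the full mITT count were the denominator and stoppers without a value fell into the not-improved group. In the 20% / 10% case the same data would then give 15.0 points on observed subjects or 9.5 points on the mITT. SAP 11.5 fixes a non-missing denominator for laboratory percentages; nothing similar is stated for the EQ-5D-5L.

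**The case against.** The strongest reply is that note E is not the only cause. The 7-day rule in SAP 8.2.3 and Table 8 footnote a would exclude later off-IMP EQ-5D-5L values even if they were collected. The key secondary mixed models likewise set data after withdrawal from IMP to missing (SAP 10.4). This stands, and it means that changing the schedule note alone would not alter the Week 25 rates. It does not make collection pointless. For the continuous key secondary endpoints, SAP 10.4.1 runs a tipping-point analysis on all data as collected; no such check is possible for the EQ-5D-5L if the values are never taken.

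The scope of note E can also be questioned: the superscript follows TSQM-9, and its companion BB concerns TSQM-9 only. But BB names TSQM-9 in its text and note E names nothing, so the plain reading is the whole row. If TSQM-9 alone was meant, the row still needs splitting.

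Three stronger conclusions might be inferred, and the documents do not support them.

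- That no later analysis can help. The stopping-visit value exists and can appear under EOT P1, and a line counting stops as not improved needs no new data.
- That Weeks 41 and 53 are affected in the same way. Study Period 1 stoppers are outside the mITT-Ex by definition and are asked to stay only to Week 25. Both sequences receive IgPro20 in Study Period 2, so there is no concurrent placebo comparison.
- That the result is shown to be biased in IgPro20's favour. The illustration moves in both directions, and staying after a stop is encouraged, not required.

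**Conclusion.** The point holds for Weeks 13 and 25. The observed improvement data and the distribution comparison for the three domains rest essentially on subjects still on IMP, with no stated strategy for IMP stops and no stated denominator.

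Size and direction cannot be derived from the documents. Under the assumed rates, equal stopping of 5% to 20% lowers a 15-point difference by about 1 to 3 points, and unequal stopping gives 9.5 to 16.0 points. These figures depend wholly on the assumed improvement rates, stop rates and improvement among stoppers.

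The importance is moderate. P-values for this endpoint are descriptive and it lies outside the gatekeeping, so neither the primary conclusion nor trial success is affected. The change is still worth making because it is cheap and makes clear what the Week 25 figures mean.

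**What to change.** 1. **Protocol Table 2.** Split the row. Keep note E for TSQM-9 only, and collect the EQ-5D-5L at its scheduled visits from subjects who stop IMP but remain in the study.
2. **SAP 10.5, supplementary analysis.** Add an EQ-5D-5L analysis of all collected values at Weeks 13 and 25. State it as an explicit exception to the 7-day rule in SAP 8.2.3 and Table 8 footnote a; otherwise the new values would be dropped.
3. **SAP 10.5, denominator.** State the denominator of the planned percentages. Add a line on the mITT denominator that counts non-war IMP stops without a value as not improved, as the primary endpoint does. Show war-related stops without a value as a separate count. This step needs no new data and can be done even if Study Period 1 collection is complete.

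The cost is a short tablet questionnaire at visits that already take place and where the HAQ is already scheduled, plus one or two extra table lines. The downside is a slight added burden on subjects who have stopped IMP.

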**Notes for the Schedule of Assessments for Study Period 3:**

- For subjects who discontinue IMP during participation in Study Period 3, all EOP3 assessments will be performed at the study visit where subjects discontinue/end study participation.
- A urine pregnancy test will be performed on all female subjects of childbearing potential.
- Vital sign assessments include supine systolic and diastolic blood pressure, pulse rate, respiratory rate, and body temperature.

- D. Hematology: hemoglobin, hematocrit, platelets, erythrocytes, leukocytes with differential counts (neutrophils, basophils, eosinophils, lymphocytes, monocytes).
- E. Biochemistry: sodium, potassium, chloride, bicarbonate, BUN, glucose, GGT, alkaline phosphatase, creatinine.
- F. Four individual CSMs will be assessed in Study Period 3: Physician Global Disease Activity and Patient Global Activity Assessment, MMT-8, and HAQ.
- G. Additional IMP will be assigned at UNS Visit if the subject's weight has increased ( $> 2$  kg), which will require a dose volume increase (see [Appendix 15](#)).
- H. IMP will be dispensed at this visit only if the subject is continuing in Study Period 3.

**Table 4** Schedule of Assessments for Rich Pharmacokinetic Sampling

Study Week	Week 37				
	Sampling Time A	+24 ± 3 h relative to the start of first infusion	+48 ± 3 h relative to the start of first infusion	+72 ± 3 h relative to the start of first infusion	+120 ± 3 h relative to the start of first infusion
Serum for IgG levels B	X	X	X	X	X
Serum for exploratory biomarkers	X	X	X	X	X

h = hours; IgG = immunoglobulin G.

**Notes to the schedule of assessments for Rich PK Sampling:**

- A. Blood draws for rich PK samples may be drawn by a phlebotomist at the subject's home where available and/or allowed by local law.
- B. The Week 37 trough level sample will be drawn at the study visit before the start of the first Week 37 dose infusion at home.
- C. The Week 37, 168-hour rich PK blood sample must be drawn before start of the first Week 38 dose infusion.

## List of Abbreviations

Abbreviation	Term
5-D	5-Dimension
AE	Adverse event
AESI	Adverse event of special interest
ALT	Alanine aminotransferase
ANA	Antinuclear antibody
AST	Aspartate aminotransferase
AUC	Area under the concentration-time curve
BDRM	Blinded Data Review Meeting
BUN	Blood urea nitrogen
C max	Maximum concentration
C trough	Trough concentration
CDASI	Cutaneous Dermatomyositis Disease Area and Severity Index
CI	Confidence interval
CIDP	Chronic inflammatory demyelinating polyneuropathy
CK	Creatine kinase
CRF	Case report form
CSLB	CSL Behring
CSM	Core set measure
CTA	Clinical trial application
CTN	Clinical trial notification
DAT	Direct antiglobulin test
DM	Dermatomyositis
DOW	Definition of Worsening
DVT	Deep vein thrombosis
eCOA	Electronic clinical outcomes assessment
ELISA	Enzyme-linked immunosorbent assay
EOP	End of Study Period
EOS	End of Study
EOT	End of Treatment
EQ-5D-5L	EuroQoL 5-Dimension Questionnaire
EULAR / ACR	European League Against Rheumatism/American College of Rheumatology
FDA	Food and Drug Administration
GCP	Good Clinical Practice

Abbreviation	Term
GMP	Good Manufacturing Practice
HAQ	Health Assessment Questionnaire
HBV	Hepatitis B virus
HCV	Hepatitis C virus
HIV	Human immunodeficiency virus
IB	Investigator's brochure
ICF	Informed consent form
ICH	International Council for Harmonisation of Technical Requirements for Pharmaceuticals for Human Use
IDMC	Independent data monitoring committee
IEC	Independent Ethics Committee
IgA	Immunoglobulin A
IgG	Immunoglobulin G
IIM	Idiopathic inflammatory myopathies
IMACS	International Myositis Assessment and Clinical Studies
IM	Intramuscular
IMP	Investigational medicinal product
IND	Investigational new drug
IRB	Institutional Review Board
IRT	Interactive response technology
IV	Intravenous
IVIG	Intravenous immunoglobulin G
LDH	Lactate dehydrogenase
MAA	Myositis-associated autoantibodies
MDAAT	Myositis Disease Activity Assessment Tool
MedDRA	Medical Dictionary for Regulatory Activities
mITT	modified Intent-to-Treat analysis set
mITT-Ex	modified Intent-to-Treat analysis set extended
MMRM	Mixed Model Repeated Measures
MMT-8	Manual Muscle Testing of 8 muscle groups
MRI	Magnetic resonance imaging
MSA	Myositis-specific autoantibodies
PE	Pulmonary embolism
PK	Pharmacokinetic analysis set
PM	Polymyositis

Abbreviation	Term
PP	Per Protocol analysis set
PT	Preferred term
SAE	Serious adverse event
SAF	Safety analysis set
SAF-Ex	Safety analysis set extended
SAP	Statistical analysis plan
SC	Subcutaneous
SCIG	Subcutaneous immunoglobulin G
SCR	Screened analysis set
SOC	System organ class
TEAE	Treatment-emergent Adverse Event
TEE	Thromboembolic event
TIS	Total Improvement Score
TSQM-9	Abbreviated Treatment Satisfaction Questionnaire for Medication
ULN	Upper limit of normal
VAS	Visual analog scale
WPAI-GH	Work Productivity and Activity Impairment Questionnaire for General Health

